4.4.2. Choice of Study Instruments

In choosing study instruments, two considerations were taken into account. First, instruments were sought that have been well-validated to assess the endpoints of interest, where available. Second, the study was tailored to be sensitive to the critical nature of these patients' illnesses and the stressful climate in which their decisions are being made. Consequently, the selected instruments will minimize the burden of participation by keeping the patient time commitment required to a minimum.

Although available tools are unable to completely capture the complexity of the construct of health literacy, the Rapid Estimate of Adult Literacy in Medicine (REALM) instrument is a validated and reliable instrument that has been extensively used in assessing health literacy, especially in the context of informed consent studies among cancer patients.^{14,15,27} The Newest Vital Sign (NVS) instrument consists of a single scenario, an ice cream container nutrition label,

and 6 questions measuring word comprehension and application and numeracy.³⁸ The REALM and NVS were chosen over other literacy assessments such as the Test of Functional Health Literacy in Adults (TOFHLA) standard and short forms because collectively they require significantly less time to administer, measure both comprehension and numeracy and are more sensitive to marginal health literacy.

The Quality of Informed Consent (QuIC) instrument will be used to measure comprehension.^{4,44} QuIC incorporates the basic elements of informed consent specified in federal regulations, assesses therapeutic misconceptions, and measures actual (part A) and perceived (part B) understanding of cancer clinical trials. It has good test-retest reliability (interclass correlation coefficient 0.66-0.77).⁴ Part A consists of 16 statements to which subjects can respond “agree”, “disagree”, or “unsure.” Part B includes 14 questions with responses measured on a 5-point scale that ranges from “I didn’t understand this at all” to “I understood this very well.” Each section is scored on a normalized scale from 0 to 100. The QuIC was chosen over other instruments that measure subject comprehension of consent forms (e.g., Brief Informed Consent Evaluation Protocol [BICEP],⁴⁵ Deaconess Informed Consent Comprehension Test [DICCT]⁴¹) as the QuIC has been developed specifically for cancer clinical trials, has been well validated in the literature, and measures both objective knowledge and self-reported subjective understanding of a subject undergoing the informed consent process in a clinical trial.^{4,8,44,46-49} As a secondary endpoint, the study will use a modification of the DICCT to evaluate subject comprehension of 8 core elements of disclosure for the study in which they are considering participation.³⁹⁻⁴¹ The test uses semi-structured interviews to obtain open-ended responses to questions related to study purpose, protocol, risks, direct benefits, indirect benefits, freedom to withdraw, alternative treatments, and voluntariness. Responses are scored as 2, 1, or 0 to indicate complete, partial, or no understanding and a composite score is determined.

Anxiety related to the consent process will be measured using the State Trait Anxiety Inventory (STAI), a commonly used and validated tool with good internal consistency, test-retest reliability.⁴² There are no validated instruments for measuring satisfaction with the informed consent process. A short questionnaire that can be self-administered by patients will be developed to measure satisfaction and understanding of key study-specific elements. In addition, selected questions will be used from the QuIC supplement to assess satisfaction.⁴³ There are no validated instruments for measuring consent information location (text search ability). To measure information location and to differentiate it from comprehension, the time it takes for subjects to locate 5 important items of information in the consent form will be determined.

4.4.3. Timing of Study Assessments

For the BMT CTN 1205 (ETRIC) study, enrolled patients will complete assessments within 7 business days of consent discussion for the parent trial. These will include assessments for health literacy and assessments for study endpoints (comprehension, anxiety, satisfaction, information location). These assessments will be conducted irrespective of whether the patient participates (and signs consent) or declines participation (and does not sign consent) for the parent study.

There are two sets of assessments:

- *Coordinator administered assessments*: These include – (1) REALM (health literacy), (2) NVS (health literacy), (3) Modified DICCT (comprehension), and (4) assessment for information location. Preferably, these assessments should occur right after the consent discussion for the parent clinical trial. However, if that is not feasible, they could be completed in a separate visit within 7 business days.
- *Patient self-administered assessments*: These will include – (1) QuIC (comprehension), (2) STAI (anxiety), and (3) assessment for satisfaction with the consent process. Preferably, these assessments should occur right after the consent discussion for the parent study. However, if that is not feasible, patients can be allowed to take them home and complete and return them by mail to the transplant center within 7 business days.

All study assessments will be administered using paper-based forms. Table 4-4-3 shows the timing of the study assessments for this study and their relation to patient reported assessments for the parentstudies.

Table 4-4-3: Patient Reported Assessments in the BMT CTN 1205 and Parent Studies

| Study/Instrument | Administered by | # of items | Within 7 business days of post-consent* | Pre-HCT ¹ | 100 Days | 180 Days | 12 mos | 24 mos | Time required |
|-----------------------------|-----------------|------------|---|----------------------|----------|----------|--------|--------|---------------|
| 1205 | | | | | | | | | |
| Health Literacy | | | | | | | | | |
| - REALM | Coordinator | 11 | X | | | | | | 2 minutes |
| - NVS | Coordinator | 6 | X | | | | | | 3 minutes |
| Comprehension | | | | | | | | | |
| - QuIC (A and B) | Self | 30 | X | | | | | | 7 minutes |
| - Modified DICCT | Coordinator | 11 | X | | | | | | 5 minutes |
| Anxiety | | | | | | | | | |
| - STAI | Self | 40 | X | | | | | | 5 minutes |
| Satisfaction | | | | | | | | | |
| - Satisfaction Survey | Self | 7 | X | | | | | | 5 minutes |
| Information location | | | | | | | | | |
| - Study specific | Coordinator | 5 | X | | | | | | 5 minutes |
| 1101 | | | | | | | | | |
| - FACT-BMT | Self | 37 | | X | | | X | X | 6 minutes |
| - MOS SF-36 | Self | 36 | | X | | | X | X | 6 minutes |
| - Global HRQoL | Self | 4 | | X | | | X | X | < 1 minute |
| - Occupational Functioning | Self | 6 | | X | | | X | X | < 1 minute |
| - EQ-5D | Self | 5 | | X | | | X | X | 1 minute |
| 1301 | | | | | | | | | |
| - FACT-BMT | Self | 37 | | X | X | X | X | X | 6 minutes |
| - MOS SF-36 | Self | 36 | | X | X | X | X | X | 6 minutes |
| - MDASI | Self | 19 | | X | X | X | X | X | < 5 minutes |

¹ Depending on a center's processes, there is a possibility that the post-consent assessments for the 1205 study and the pre-transplant assessments for the 1101 or 1301 study will occur at the same time.

Note: There are no patient-reported assessments for the BMT CTN 1203.

4.5. Study Monitoring

Monitoring for this study will follow the mechanisms already established for the parent trials, whichever trial the patient is being considered for. Given the minimal risks associated with the BMT CTN 1205 (ETRIC) study interventions and the subsequent short followup period, no additional monitoring will be conducted for the BMT CTN 1205 (ETRIC) study. Patients will be monitored clinically with laboratory assessments, physical exams, restaging studies, and other testing deemed to be standard practice and appropriate by the treating physician and the transplant center.

4.5.1. Case Report Forms

The procedures required for forms completion and timeliness of submission can be found in the AdvantageEDCSM User's Guide. Assessments that are not completed in AdvantageEDCSM within 30 days of participant enrollment onto 1205 are considered delinquent. Transplant centers can view submitted past due and expected forms via AdvantageEDCSM. A missing form will continue to be requested either until the form is reported or until an exception is granted.

4.5.2. Reporting Patient Deaths

Patient deaths related to the BMT CTN 1205 (ETRIC) study are not anticipated. Reporting of patient death to the BMT CTN Data and Coordinating Center (DCC) will be conducted according to established procedures for the parent trials.

4.5.3. Reporting Serious Adverse Events

Reporting of patient serious adverse events (SAE) will be consistent with standard BMT CTN procedures but be limited to events which are possibly, probably, or definitely associated with participation in this study since this protocol does not involve any pharmacologic treatment or invasive procedures. Unexpected, grades 3-5 adverse events (AEs) will be reported through an expedited AE reporting system via the web-based electronic data capture system, AdvantageEDC. Unexpected, grades 4-5 AEs must be reported within 24 hours of the event. Unexpected, grade 3 AEs must be reported within three business days of knowledge of the event. Other SAEs will be tracked periodically as defined in the Form Submission Schedule, staged according to NCI Common Terminology Criteria for Adverse Events (CTCAE), Version 4.0. The Data and Safety Monitoring Board will receive summary reports of all adverse experiences on at least an annual basis.

4.5.4. CIBMTR Data Reporting

Centers participating in BMT CTN trials must register and provide transplant outcome data on all consecutive hematopoietic stem cell transplants done at their institution during their time of BMT CTN participation to the Center for International Blood and Marrow Transplant Research (CIBMTR). Registration is done using procedure and forms developed by CIBMTR for the Stem Cell Transplant Outcomes Database (SCTOD). (Note: Federal legislation requires submission of these forms for all US allogenic transplant recipients.)

Patients enrolled in this trial will remain on pre selected form submission track (Transplant Essential Data track also known as “TED” track or Comprehensive Report Form track also known as “CRF” track) that was originally assigned by the CIBMTR algorithm. CIBMTR forms will be submitted directly to the CIBMTR at the times specified on the Form Submission Schedule.

CHAPTER 5

5. STATISTICAL CONSIDERATIONS

5.1. Study Design for Randomized Study

The randomized study will test two interventions – the ETRIC consent form vs. the standard consent form for patients participating in the BMT CTN 1101 and 1301 studies. The BMT CTN 0901 trial and BMT CTN 1203 trial were removed as parent protocols for the BMT CTN 1205 study due to their closure to accrual on April 18, 2014 and May 13, 2016, respectively. Those who enrolled in the BMT CTN 1205 prior to the BMT CTN 0901 and BMT CTN 1203 closures will be included in the analysis.

5.1.1. Accrual

It is estimated that 3 years of accrual will be necessary to enroll the targeted sample size of 198 patients (99 in each arm). Accrual will be reported by race, ethnicity, and sex. Study assessments will be conducted after the consent process. No patient follow-up will be conducted for this study.

5.1.2. Randomization

Patients will be randomized at a ratio of 1:1 between the two consent arms. Randomization will be stratified by center and by parent BMT CTN treatment protocol. Study ID numbers will be randomized within strata. Study personnel will be blinded to randomization assignment until a study participant agrees to participate and is assigned a study ID number.

5.1.3. Study Endpoints

The primary endpoint of this study is to compare objective comprehension scores on the QuIC (part A) instrument between patients randomized to the ETRIC versus the standard consent arms. Secondary endpoints will compare the following measures between the two arms: (1) subjective comprehension scores on the QuIC (part B) instrument and the modified DICCT instrument, (2) state anxiety scores on STAI instrument, (3) satisfaction scores, (4) time taken for information location, and (5) patient consent rates on parent clinical trials.

5.2. Sample Size and Power Calculations

Based on previous studies in the literature,^{4,43,44} this study is designed to detect a 4-point difference in the mean QuIC part A comprehension scores between the two study arms. This difference represents a 0.5 standard deviation difference and has been considered to represent a clinically meaningful difference in comprehension scores in previous studies. The sample size for a two-sample t-test will require 64 participants per group to detect a 4-unit difference between group means ($\alpha=5\%$, power=80%, standard deviation=8). Asymptotic relative efficiency of the Mann-Whitney test to the 2-sample t-test is 0.864 under any symmetric

distribution, which means that 15% more subjects will need to be recruited, leading to 74 per group or 148 in total. Another 25% is added to account for possible dropouts (e.g., patients consent for this study, but are subsequently not able to participate in the consent process for the BMT CTN parent clinical trial [e.g., due to disease progression or determined ineligible to participate]). The study will need to enroll 198 subjects (approximately 99 in each arm). The stratified randomization will eliminate possible association between trial and center strata and consent group assignment, which potentially increases power properties.

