BMT CTN #1205 Statistical Analysis Plan (SAP)

Drafted by: [name] on 9/17/16

PROTOCOL: Easy-to-Read Informed Consent (ETRIC) for Hematopoietic Cell Transplantation Clinical Trials

Protocol Synopsis:

The BMT CTN protocol #1205 titled “Easy-to-Read Informed Consent (ETRIC) for Hematopoietic Cell Transplantation Clinical Trials” is a randomized, multicenter, prospective comparative study of ETRIC or standard consent form to improve patient comprehension of BMT CTN parent clinical trials. The primary objective is to compare objective comprehension scores on the Quality of Informed Consent (part A) instrument between patients randomized to the ETRIC versus the standard consent arms. Secondary objectives are to compare the following measures between the two arms: (1) subjective comprehension scores on the Quality of Informed Consent (part B) instrument and the modified Deaconess Informed Consent Comprehension Test instrument, (2) state anxiety scores on State Trait Anxiety Inventory instrument, (3) satisfaction score, (4) time taken for information location, and (5) patient consent rates on parent clinical trials. Per the original study design, the target sample size was 160 patients with 80 on each arm ensuring 64 patients per arm to complete Quality of Informed Consent part A comprehension survey. An interim analysis revealed that the survey completion rate was lower than expected, and then the target sample size was increased to 198 with expected 99 patients per group and 64 per arm to complete the Quality of Informed Consent part A questionnaire.

Study Status and Publication Plan:

The study opened enrollment in November 2013 and closed in August 2016 when the targeted sample of 198 patients was enrolled. Two manuscripts are anticipated from this trial. The first manuscript will describe the qualitative study and will detail the barriers and facilitators that were identified on semi-structured interviews of participating site research and IRB personnel. The analysis for this manuscript has been completed. The second manuscript will present the analysis of the randomized study that is detailed in this statistical analysis plan. We plan to circulate the first draft of the manuscript to the protocol team for review within 6 weeks after the analysis has been reviewed.

Survey instrument scoring:

- The Quality of Informed Consent Parts A and B will be scored as described in (Joffe et al, 2001)

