- The Rapid Estimate of Adult Literacy Revised (REALM-R, a health literacy measure) will be scored as described in (Bass et all, 2003): words “fat”, “flu”, and “pill” will not be scored.
- The New Vital Sign (a health literacy measure) will be scored as described in (Weiss et al, 2005)
- The State-Trait Anxiety Inventory (STAI) will be scores as described in its manual (Spielberger et al, 1983)

NCT02081248

- The Consent Form Satisfaction Survey will be summarized by its total score as the sum of responses to its seven Likert questions (0-4).
- The Deaconess Informed Consent Comprehension Test will be scored as described in (Miller et al, 1996). The total score ranges between 0-28.

Primary Endpoint and Data Analysis:

The primary endpoint of BMT CTB 1205 is the mean comprehension score on the Quality of Informed Consent (part A) instrument.

The primary analysis will be performed using all patients who completed the Quality of Informed Consent (Part A) and will be based on the two sample t-test or, if the t-test assumptions are violated, with Mann-Whitney test. The statistical significance will be declared if the P-values of a two-sided test <0.05 .

The following non-primary analyses will use all randomized patients with possible exclusion of clinical trials protocols with high missing data rates. Non-primary analysis will rely on linear regression models with multiple imputations to address missing data issues.

Analysis of interactions between the randomized assignment and (1) the trial protocol, (2) literacy level (REALM-R), (3) income, (4) age groups, (5) education level. The statistical significance of interactions will be declared at ALPHA 0.01 (Bonferroni adjustment for 5 tests). If the interaction test is significant then post-hoc comparisons between the ETRIC and standard consent groups will be performed for each level of a categorical variable.

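### The Mann-Whitney efficiency of 0.864 in section 5.2 is a lower bound, and the SAP's 64 completers per arm drop the allowance built on it, leaving the fallback test at about 74% to 78% power

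*Protocol*

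**What the plan says.** Protocol section 5.2 sets the target: "this study is designed to detect a 4-point difference in the mean QuIC part A comprehension scores between the two study arms". It adds that "This difference represents a 0.5 standard deviation difference" and that "The sample size for a two-sample t-test will require 64 participants per group to detect a 4-unit difference between group means", with alpha 5% and "power=80%, standard deviation=8".

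It then allows for a rank test. The reason given is that "Asymptotic relative efficiency of the Mann-Whitney test to the 2-sample t-test is 0.864 under any symmetric" distribution, from which it concludes that "15% more subjects will need to be recruited, leading to 74 per group or 148 in total". A further 25% for dropout gives 198 enrolled, about 99 per arm. The section does not describe 0.864 as a minimum. The protocol synopsis, under Statistical Issues, attaches 80% power to the 198 patients.

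Protocol section 5.5 and the SAP's primary analysis both use the t-test, with Mann-Whitney if the t-test assumptions fail. The SAP bases the primary analysis on patients who completed QuIC part A.

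The SAP synopsis explains 198 differently. The first target was 160, meant to yield 64 completers per arm. Completion was lower than expected, so enrolment rose to 198, still with "64 per arm to complete the Quality of Informed Consent part A questionnaire". It mentions no rank-test allowance and gives no power figure.

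**The concern.** Two things do not fit together.

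First, the efficiency of Mann-Whitney relative to the t-test is not one number for all symmetric distributions. A reader who takes section 5.2 literally will think that the rank test needs 74 per group whatever the shape of the scores. In fact 74 is needed only in the least favourable case.

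Second, the protocol treats 74 completers per arm as necessary if the fallback test is used, while the SAP plans for 64. Both documents reach 198 enrolled, so the difference is easy to miss. At stake is whether the stated 80% power covers the whole primary analysis, including its fallback, or only the t-test.

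**Working it through.** **Inputs.** Difference 4, SD 8, so d = 0.5; alpha 5%; power 80%; 64 and 74 per group; efficiency 0.864; 25% loss (all protocol section 5.2). The two-sided test comes from the SAP: "The statistical significance will be declared if the P-values of a two-sided test" fall below 0.05. The 64 completers per arm come from the SAP synopsis.

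**Reproducing the plan's figures.**
- t-test, noncentral t: 63.77, so 64 per group.
- Rank-test allowance: 64/0.864 = 74.07 and 64 × 1.15 = 73.6. From the unrounded value, 63.77/0.864 = 73.8. All give 74 per group, 148 in total.
- Loss: 148/0.75 = 197.3, so 198.

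Every figure reproduces.

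**Efficiency by shape.** For a continuous score and a pure shift, efficiency = 12 σ² (∫f²)².
- Normal: ∫f² = 1/(2σ√π), so 12/(4π) = 3/π = 0.955.
- Uniform: 1.000.
- Logistic: π²/9 = 1.097.
- Double-exponential: 1.5.
- Parabolic density on ±√5 (σ = 1): ∫f² = 0.12√5, so 12 × 0.072 = 0.864. This is the least favourable case.

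**Power.** The effective size per group is m = n × efficiency. Power comes from the noncentral t with 2(m − 1) degrees of freedom and noncentrality 0.5 × √(m/2). For example, 64 × 0.864 = 55.3 gives noncentrality 2.63 and power 74.1%, and 64 × 0.955 = 61.1 gives 2.76 and 78.3%. Simulation used 20,000 runs per setting.

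| Test and score shape | 64 per arm: formula / simulation | 74 per arm: formula / simulation |
|---|---|---|
| t-test | 80.1% / not run | 85.6% / not run |
| Mann-Whitney, parabolic (worst case) | 74.1% / 74.2% | 80.1% / 79.6% |
| Mann-Whitney, normal | 78.3% / 78.0% | 83.9% / 83.9% |
| Mann-Whitney, uniform | 80.1% / 76.0% | 85.6% / 81.7% |
| Mann-Whitney, logistic | 83.7% / 82.9% | 88.6% / 88.3% |
| Mann-Whitney, double-exponential | 93.1% / 91.2% | 96.0% / 94.3% |

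The uniform row shows that the asymptotic formula can be a few points too high at these sizes.

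**Where the two documents part.** The protocol's loss leaves 99 × 0.75 = 74 per arm. The SAP's 64 of 99 is 64.6%, a loss of about 35%. The SAP's missing-data paragraph expects about two thirds to complete. That is 66 per arm, where Mann-Whitney power is 75.4% (worst case) to 79.5% (normal), still under 80%.

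**The case against.** The strongest reply is that planning on a distribution-free lower bound is a sound, conservative choice. That stands. A reader might infer from the faulty sentence that 74, 148 and 198 are wrong and should be replaced by the normal-score requirement (63.77/0.955 = 66.8, so 67 per group and about 180 enrolled). The documents do not support that. Mann-Whitney is reserved for the case where the t-test assumptions fail, so a normal-score efficiency is not the obvious planning value for it, and 74 follows correctly from the bound.

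It can also be said that with normal scores the t-test would be used and 64 completers suffice. That is true, and it is why the 80% figure holds for the t-test. It does not rescue the fallback, which is part of the primary analysis and for which the protocol itself added 15%.

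Finally, the gap between 74 and 64 exists however 0.864 is described. This is also correct. The wording does not cause the gap, but anyone stating power at 64 completers needs the right efficiency. Read literally, section 5.2 implies about 74% for every symmetric shape, when that is the floor.

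**Conclusion.** The concern holds as a correction to the wording and an unstated power figure. Section 5.2 presents a minimum as a general value. Its sample sizes stand as worst-case figures, with 80% at 74 completers a floor and about 84% for normal scores. At the SAP's 64 completers per arm, 80% applies to the t-test (80.1%). For the Mann-Whitney fallback, power is about 78% for normal scores and about 74% in the worst case, a shortfall of roughly 2 to 6 points.

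A reader might infer that the fallback is always underpowered at 64. It is not: heavy-tailed symmetric scores take it above 80%.

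These figures assume d = 0.5, a two-sided 5% test, a continuous score and a pure shift. QuIC part A has 16 three-option items, so ties make them approximate, and the documents do not give the shape of its distribution. The point is minor. The SAP reports enrolment closed at 198, so it bears on how power is reported.

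**What to change.** In protocol section 5.2, change the efficiency statement to: *at least 0.864 for a continuous score under a shift (0.955 for normal scores)*. Keep 74, 148 and 198, described as worst-case figures.

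In section 5.2 and the SAP synopsis, add that 64 completers per arm give 80% power for the t-test and about 74% (worst case) to 78% (normal scores) for Mann-Whitney. Note that heavier tails give more, and that the values are asymptotic and approximate for a 16-item score.

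The cost is a few sentences. Enrolment and the choice of test do not change.
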